8.4. Treatment of Overdose

For the purposes of this study, and overdose of lasmiditan, dabigatran etexilate, or rosuvastatin is considered any dose higher than the dose assigned. There is no specific antidote for lasmiditan, or rosuvastatin.

In the event of an overdose, the investigator/treating physician should:

1. contact the medical monitor immediately.
2. closely monitor the participant for any AE/SAE and laboratory abnormalities until study intervention can no longer be detected systemically (at least 2 days).
3. document the quantity of the excess dose as well as the duration of the overdose in the CRF.
4. in the case of emergency uncontrolled bleeding as a direct consequence of dabigatran, urgent referral for treatment with idarucizumab should be considered.

Decisions regarding dose interruptions or modifications will be made by the investigator in consultation with the medical monitor based on the clinical evaluation of the participant.

8.5. Pharmacokinetics

At the visits and times specified in the SoA, venous blood samples of approximately 2 mL each will be collected to determine the plasma concentrations of lasmiditan, metabolite M8, rosuvastatin, and dabigatran. A maximum of 3 samples may be collected at additional time points during the study if warranted and agreed upon between both the investigator and sponsor. Instructions for the collection and handling of blood samples will be provided by the sponsor. The actual date and time (24-hour clock time) of each sampling will be recorded.

8.5.1. Bioanalysis

Samples will be analyzed at a laboratory approved by the sponsor and stored at a facility designated by the sponsor.

Concentrations of lasmiditan, metabolite M8, rosuvastatin, and dabigatran will be assayed using a validated liquid chromatography with tandem mass spectrometry method.

Bioanalytical samples collected to measure study intervention concentrations will be retained for a maximum of 2 years following last participant visit for the study.

8.6. Pharmacodynamics

Pharmacodynamic parameters are not evaluated in this study.

8.7. Genetics

A blood or saliva sample for DNA isolation will be collected from participants.

See Appendix 10.5 for information regarding genetic research and Appendix 10.1.10 for details about sample retention and custody.

8.8. Biomarkers

Biomarkers are not evaluated in this study.

8.9. Immunogenicity Assessments

Not applicable for this study.

8.10. Health Economics

This section is not applicable for this study.

9. Statistical Considerations

9.1. Statistical Hypotheses

There is no direct control for multiplicity but both primary objective variables will be tested as co- confirmatory variables. All other tests and/or estimation statistics will not be confirmatory but will contribute to a body of evidence to support final conclusions.

No significant DDI for dabigatran or rosuvastatin will be concluded if the respective 90% confidence interval for AUC from time zero to infinity (AUC[0- ∞]) and C_{max} is completely contained within the no-effect boundaries (0.80, 1.25). A description of each test is provided in Section 9.4.

9.2. Sample Size Determination

Approximately 72 participants will be enrolled to Part 1 of the study to ensure that at least 62 evaluable participants complete that part. With 62 participants, we expect the two 1-sided t-tests (TOSTs) for equivalence applied to the lognormal mean ratio to have a power of at least 80% for the AUC(0- ∞) and C_{max} tests in Part 1. This assumes a nominal expected mean ratio of 1.05, a coefficient of variation (CV) of 39.3%, and a significance level of 0.05 of each 1-sided test when testing against an upper limit of 1.25 and a lower limit of 0.80. The tests will be displayed in the form of 90% confidence intervals, which are equivalent to the according TOST. The source of the CV is Boehringer Ingelheim bioequivalence study (EudraCT number 2007-005765-35), and the higher intrasubject CV observed in the second-generation dabigatran arm was chosen.

Approximately 32 participants will be enrolled to Part 2 to ensure that at least 28 evaluable participants complete that part. With 28 participants, we expect the two 1-sided t-tests for equivalence applied to the lognormal mean ratio to have a power of at least 80% for the AUC(0- ∞) and C_{max} tests in Part 2. This assumes a nominal expected mean ratio of 1.05, a CV of 25.1%, and significance level of 0.05 of each 1-sided test when testing against an upper limit of 1.25 and a lower limit of 0.80. The tests will be displayed in the form of 90% confidence intervals which are equivalent to the according TOST. The source of the CV is Study AZEB, and the higher of the rosuvastatin AUC(0- ∞) and C_{max} intrasubject CVs was chosen.

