4.1.1. Number of Participants

Approximately 72 participants will be enrolled to Part 1 of the study to ensure that at least 62 evaluable participants complete that part. Approximately 32 participants will be enrolled to Part 2 to ensure that at least 28 evaluable participants complete that part. For the purposes of this study, a participant completes the study when all scheduled procedures shown in the Schedule of Activities (Section 1.3) have been finished.

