## 7. SAMPLE SIZE JUSTIFICATION

Approximately 72 participants will be enrolled to Part 1 of the study to ensure that at least 62 evaluable participants complete that part. With 62 participants, we expect the two 1-sided t-tests (TOSTs) for equivalence applied to the log-normal mean ratio to have a power of at least 80% for the AUC (0- $\infty$ ) and Cmax tests in Part 1. This assumes a nominal expected mean ratio of 1.05, a coefficient of variation (CV) of 39.3%, and a significance level of 0.05 of each 1-sided test when testing against an upper limit of 1.25 and a lower limit of 0.80. The tests will be displayed in the form of 90% confidence intervals (CI), which are equivalent to the according TOST. The source of the CV is Boehringer Ingelheim bioequivalence study (EudraCT number 2007-005765-35), and the higher intrasubject CV observed in the second-generation dabigatran arm was chosen.

Approximately 32 participants will be enrolled to Part 2 to ensure that at least 28 evaluable participants complete that part. With 28 participants, we expect the TOSTs for equivalence applied to the lognormal mean ratio to have a power of at least 80% for the AUC(0- $\infty$ ) and Cmax tests in Part 2. This assumes a nominal expected mean ratio of 1.05, a CV of 25.1%, and significance level of 0.05 of each 1-sided test when testing against an upper limit of 1.25 and a lower limit of 0.80. The tests will be displayed in the form of 90% CI which are equivalent to the according TOST. The source of the CV is Study AZEB, and the higher of the rosuvastatin AUC(0- $\infty$ ) and Cmax intrasubject CVs was chosen.

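### Is the stated power of at least 80% short of what the rule requiring both AUC(0-∞) and Cmax to pass needs?

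*Protocol*

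**What the plan says.** Protocol 9.2 describes tests "applied to the lognormal mean ratio to have a power of at least 80% for the" AUC(0-∞) and Cmax comparisons; SAP section 7 repeats it ("applied to the log-normal mean ratio to have a power of at least 80% for the"). Each part is planned on a ratio of 1.05, one-sided α of 0.05, limits 0.80 and 1.25, and a single CV: 39.3% in Part 1 and 25.1% in Part 2.

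In Part 1, "the higher intrasubject CV observed in the second-generation dabigatran arm was chosen". In Part 2 the text reads "The source of the CV is Study AZEB, and the higher of the rosuvastatin" AUC(0-∞) and Cmax values. The lower CV is not given for either part.

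Enrolment in Part 1 is about 72, "to ensure that at least 62 evaluable participants complete that part". Part 2 enrols about 32 to obtain at least 28.

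On the decision, Protocol 9.1 says "both primary objective variables will be tested as co- confirmatory variables", and concludes no significant interaction for a substrate if the 90% confidence interval for AUC(0-∞) and Cmax "is completely contained within the no-effect boundaries (0.80, 1.25".

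**The concern.** The conclusion for each substrate needs two intervals inside the limits, but the power paragraph uses one CV and one ratio. The chance of passing two tests cannot exceed the chance of passing the harder one and is usually lower. The evaluable numbers are also the smallest that reach 80% for one test, so they leave almost no room: 0.2 percentage points in Part 1 and 1.4 in Part 2.

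A reader who takes the 80% as the chance of a no-interaction conclusion could therefore be too optimistic. That would matter if a part passed on one parameter and narrowly missed on the other, because the miss might then be read as evidence of an interaction when it reflected limited power.

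**Working it through.** **Inputs.** Ratio, CVs, α, limits and evaluable numbers come from Protocol 9.2. The paired structure comes from Protocol 4.2 (each participant is his or her own control). The model in SAP 9.3.2 has treatment fixed and participant random, which with complete pairs is a paired t analysis of log differences.

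**Per-test power.** On the log scale:

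- σ² = ln(1 + CV²), SE = σ√(2/n), df = n − 1
- The test passes if the estimate ± t(0.95, df) × SE lies between ln 0.80 = −0.2231 and ln 1.25 = 0.2231, with the true difference at ln 1.05 = 0.0488. Power is integrated over the chi-square distribution of the estimated variance.

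Part 1: σ² = ln(1 + 0.393²) = 0.1436, σ = 0.3790, SE = 0.3790 × √(2/62) = 0.0681, t = 1.670. Power is **80.2%** (n = 61 gives 79.6%).

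Part 2: σ² = ln(1 + 0.251²) = 0.0611, σ = 0.2472, SE = 0.2472 × √(2/28) = 0.0661, t = 1.703. Power is **81.4%** (n = 27 gives 79.9%).

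The stated figure reproduces, and 62 and 28 are the smallest numbers that reach 80% for one test.

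**Power to pass on both.** This needs two further inputs that the documents do not give: the correlation between the log differences in AUC(0-∞) and Cmax, and the CV of the less variable parameter. Both are assumed over ranges here.

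With zero correlation and equal CVs the answer is the square of the per-test power: 0.802² = 0.643 and 0.814² = 0.663. Other cases were simulated with 400,000 trials each (Monte Carlo error under 0.1 point), at ratio 1.05 for both parameters and the minimum evaluable number. Joint power, %:

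| Part | Second CV | corr. 0 | 0.5 | 0.8 | 0.9 | 0.95 |
|---|---|---|---|---|---|---|
| 1 (n = 62) | equal | 64.3 | 68.4 | 72.8 | 74.8 | 76.4 |
| 1 | 10% lower | 69.8 | 73.3 | 76.6 | 78.3 | 79.4 |
| 1 | 20% lower | 74.7 | 76.9 | 79.0 | 79.9 | 80.2 |
| 1 | 30% lower | 78.0 | 79.1 | 79.9 | 80.2 | 80.2 |
| 2 (n = 28) | equal | 66.3 | 70.2 | 74.1 | 76.2 | 77.7 |
| 2 | 10% lower | 71.8 | 74.9 | 78.1 | 79.7 | 80.7 |
| 2 | 20% lower | 76.7 | 78.5 | 80.4 | 81.1 | 81.4 |
| 2 | 30% lower | 79.5 | 80.6 | 81.3 | 81.4 | 81.4 |

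**Sensitivity to the other assumptions** (correlation 0 to 0.9):

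- True ratio 1.00, equal CVs, minimum n: 79.2–85.0% in Part 1 and 81.0–86.3% in Part 2.
- All 72 and 32 enrolled evaluable, ratio 1.05, equal CVs: 73.6–81.6% and 74.6–82.2%.
- The same with the second CV 10% lower: 78.3–84.4% and 79.5–85.1%.

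**Type I error.** Requiring both tests to pass cannot raise the chance of a false no-interaction conclusion above the level of one test, so only power is in question.

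**The case for a change.** The strongest argument for a change is that the combined rule is the one that decides, and its power is missing. The sizes were set for one test, and nothing in either document says so outright. With equal CVs, joint power stays below 80% even at a correlation of 0.99 (78.7% and 79.6%). In Part 1 the 0.2-point margin means that, at 62 evaluable and a ratio of 1.05, the combined rule reaches 80% only near the favourable end of the range. The remedy would be a label and one sentence.

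These facts stand, but they do not show that the plan misses a power it claims. The wording refers to the tests in the plural, gives α for each one-sided test, and uses one CV and no correlation; that describes a per-test calculation. The planning CV is the higher one, so equal CVs are the pessimistic boundary. Positive correlation is to be expected because both measures come from the same concentration profile, although no value is documented. The evaluable numbers are minimums: with 67 evaluable in Part 1, midway to 72, joint power is 80.1% if the second CV is 10% lower and the correlation is 0.8.

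An added sentence on joint power would still rest on an assumed correlation. Nobody would run or analyse the trial differently because of it.

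**Conclusion.** The stated power is correct as a per-test figure: 80.2% in Part 1 and 81.4% in Part 2. The power of the both-must-pass rule is an unstated quantity, not an error. At ratio 1.05 and the minimum evaluable numbers it cannot exceed those figures. It could be as low as about 64% and 66%, but only with zero correlation and equal CVs. Non-negative correlation is assumed throughout, and the true values probably lie in the upper part of each range.

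No change follows. The sample size, decision rule, type I error, ratios and 90% confidence intervals would all stay the same. If one parameter narrowly fails, its ratio and interval are reported and show whether the result is inconclusive or points to an interaction. Labelling the figure as per test would be a harmless courtesy to the reader, but the plan does not depend on it.

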9.3. Populations for Analyses

The following populations are defined:

Population	Description
Entered	All participants who sign the ICF
Enrolled	All participants assigned to treatment, regardless of whether they take any doses of study intervention, or if they took the correct treatment.
Safety	All participants assigned to dabigatran etexilate or rosuvastatin and who take at least 1 dose of 1 of those products. Participants will be analyzed according to the product they actually received.

Pharmacokinetic Analysis	All participants who receive at least 1 dose of dabigatran etexilate or rosuvastatin and have evaluable PK.
--------------------------	-------------------------------------------------------------------------------------------------------------

9.3.1. Study Participant Disposition

A detailed description of participant disposition will be provided at the end of the study.

9.3.2. Study Participant Characteristics

The subject's age, sex, and other demographic characteristics will be recorded and summarized. Demographic characteristics may be considered in the interpretation of PK and safety analyses.

9.3.3. Treatment Compliance

The date and time of dosing will be recorded and listed.

9.4. Statistical Analyses

Statistical analysis of this study will be the responsibility of the sponsor or its designee.

Pharmacokinetic analyses will be conducted on data from all participants who receive at least 1 dose of lasmiditan and have evaluable PK. Statistical inference of PK parameters will utilize participants in the PK analysis population which have evaluable PK, both before and after the introduction of lasmiditan.

Safety analyses will be conducted for all enrolled participants who received at least 1 dose of dabigatran etexilate or rosuvastatin, whether or not they completed all protocol requirements.

Additional exploratory analyses of the data will be conducted as deemed appropriate.

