### **3. INTRODUCTION**

This SAP has been developed after review of the Clinical Study Protocol (final version dated 11 September 2020) and Protocol Amendment (a) (final version dated 16 September 2020).

This SAP describes the planned analysis of the safety, tolerability and pharmacokinetic (PK) data from this study. A detailed description of the planned TFLs to be presented in the clinical study report (CSR) is provided in the accompanying TFL shell document.

The intent of this document is to provide guidance for the statistical and PK analyses of data. In general, the analyses are based on information from the protocol, unless they have been modified by agreement with Eli Lilly and Company. A limited amount of information concerning this study (e.g., objectives, study design) is given to help the reader's interpretation. This SAP must be signed off prior to first participant visit for this study. When the SAP and TFL shells are agreed upon and finalized, they will serve as supporting material for this study's CSR.

This SAP supersedes the statistical considerations identified in the protocol; where considerations are substantially different, they will be so identified. If additional analyses are required to supplement the planned analyses described in this SAP, they may be performed and will be identified in the CSR. Any substantial deviations from this SAP will be agreed upon with Eli Lilly and Company and identified in the CSR. Any minor deviations from the TFLs may not be documented in the CSR.

This SAP is written with consideration of the recommendations outlined in the International Conference on Harmonisation (ICH) E9 Guideline entitled Guidance for Industry: Statistical Principles for Clinical Trials and the ICH E3 Guideline entitled Guidance for Industry: Structure and Content of Clinical Study Reports.

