## 8. DEFINITION OF ANALYSIS POPULATIONS

The “Entered” population will consist of all participants who signed the informed consent form (ICF).

The “Enrolled” population will consist of all participants assigned to treatment, regardless of whether they take any doses of study intervention, or if they took the correct treatment.

The “Safety” population will consist of all participants assigned to dabigatran etexilate or rosuvastatin and who take at least 1 dose of 1 of those products. Participants will be analyzed according to the product they actually received.

---

The “Pharmacokinetic” population will consist of all participants who receive at least 1 dose of dabigatran etexilate or rosuvastatin and have evaluable PK.

All protocol deviations that occur during the study will be considered for their severity/impact and will be taken into consideration when participants are assigned to analysis populations.

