## **9. STATISTICAL METHODOLOGY**

### **9.1 General**

Data listings will be provided for all data that is databased. Summary statistics and statistical analysis will only be presented for data where detailed in this SAP. For continuous data, summary statistics will include the arithmetic mean, arithmetic standard deviation (SD), median, min, max and N; for log-normal data (e.g. the PK parameters: AUCs and  $C_{max}$ ) the geometric mean and geometric CV will also be presented. For categorical data, frequency count and percentages will be presented. Data listings will be provided for all participants up to the point of withdrawal, with any participants excluded from the relevant population highlighted. Summary statistics and statistical analyses will generally only be performed for participants included in the relevant analysis population. For the calculation of summary statistics and statistical analysis, unrounded data will be used.

Mean change from baseline is the mean of all individual participants' change from baseline values. Each individual change from baseline will be calculated by subtracting the individual participant's baseline value from the value at the timepoint. The individual participant's change from baseline values will be used to calculate the mean change from baseline using a SAS procedure such as PROC UNIVARIATE.

Data analysis will be performed using SAS® Version 9.4 or greater.

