### General PK Parameter Rules

- Actual sampling times will be used in the final analyses of individual PK parameters, except for non-bolus pre-dose sampling times which will be set to zero.
- Cmax and tmax will be reported from observed values. If Cmax occurs at more than one time point, tmax will be assigned to the first occurrence of Cmax.
- AUC parameters will be calculated using a combination of the linear and logarithmic trapezoidal methods (linear-log trapezoidal rule). The linear trapezoidal method will be applied up to tmax and then the logarithmic trapezoidal method will be used after tmax. The minimum requirement for the calculation of AUC will be the inclusion of at least three consecutive plasma concentrations above the lower limit of quantification (LLOQ), with at least one of these concentrations following Cmax. AUC(0-∞) values where the percentage of the total area extrapolated is more than 20% will be flagged. Any AUC(0-∞) value excluded from summary statistics will be noted in the footnote of the summary table.
- Half-life (t1/2) will be calculated, when appropriate, based on the apparent terminal log-linear portion of the concentration-time curve. The start of the terminal elimination phase for each participant will be defined by visual inspection and generally will be the first point at which there is no systematic deviation from the log-linear decline in plasma

concentrations. Half-life will only be calculated when a reliable estimate for this parameter can be obtained comprising of at least 3 data points. If  $t_{1/2}$  is estimated over a time window of less than 2 half-lives, the values will be flagged in the data listings. Any  $t_{1/2}$  value excluded from summary statistics will be documented in the footnote of the summary table.

- A uniform weighting scheme will be used in the regression analysis of the terminal log-linear portion of the concentration-time curve.
- The parameters based on predicted  $C_{last}$  will be reported.

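### Do the differing pharmacokinetic population rules in the protocol and SAP put the primary comparisons in doubt?

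*Protocol*

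**What the plan says.** Protocol section 9.3 gives the PK analysis population as "All participants who receive at least 1 dose of dabigatran etexilate or rosuvastatin and have evaluable PK". SAP section 8 uses the same definition: the population "will consist of all participants who receive at least 1 dose of dabigatran etexilate or rosuvastatin and have evaluable PK".

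Protocol section 9.4 adds two statements. The first is "Pharmacokinetic analyses will be conducted on data from all participants who receive at least 1 dose of lasmiditan and have evaluable PK". The second restricts statistical inference to those in the PK analysis population "which have evaluable PK, both before and after the introduction of lasmiditan".

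The SAP repeats neither. Its section 9.1 says "Summary statistics and statistical analyses will generally only be performed for participants included in the relevant analysis population", and section 8 names only one PK population. Section 9.3.2 fits log Cmax and log AUC(0-∞) with a fixed treatment effect and a random participant effect, and the example code has no filter on completeness.

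On precedence, SAP section 3 says "In general, the analyses are based on information from the protocol, unless they have been modified by agreement with" the sponsor. It also says "This SAP supersedes the statistical considerations identified in the protocol; where considerations are substantially different, they will be so identified". SAP section 11 reports no changes.

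**The concern.** A participant dosed on Day 1 who leaves before Day 8 is inside the SAP population and outside both sets in Protocol section 9.4. A random-participant model uses one-period records, so two programmers could run the primary model on different participants and report different counts and confidence intervals. The result at stake is the primary conclusion: whether each 90% interval lies within 0.80 to 1.25.

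The same question could arise with no dropout. SAP section 9.3.1 lets single values be dropped. For AUC(0-∞), any "value excluded from summary statistics will be noted in the footnote of the summary table", and the outlier procedure can remove one individual value. No sentence says whether the same participant's value from the other period stays in the model. A value removed because it is extreme is not missing at random, so the usual justification for an all-available mixed model does not cover that case.

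The statement in SAP section 11 is also a weak guarantee that the protocol rule was kept. It is inaccurate elsewhere: SAP section 9.4.5 does not present ECGs and section 9.4.7 only lists C-SSRS data, whereas Protocol sections 9.4.1.2 and 9.4.5 call for summaries.

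**Working it through.** **Who falls in which set**

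| Participant | Protocol 9.3 and SAP 8 | Protocol 9.4, PK analyses | Protocol 9.4, inference |
|---|---|---|---|
| Evaluable in both periods | in | in | in |
| Leaves before Day 8 | in | out | out |
| Takes lasmiditan on Day 8, leaves before Day 10 | in | in | out |

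The definitions clash only in the second row, first two columns, which is a matter of descriptive output. The inference set is drawn from the PK population, so it narrows Protocol 9.3 and SAP 8 without contradicting them.

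**The plan's own sample size.** Inputs from Protocol section 9.2: ratio 1.05, CV 39.3% (Part 1) and 25.1% (Part 2), limits 0.80 and 1.25, one-sided 0.05. Within-participant log SD = √ln(1+CV²); paired SE = SD × √(2/n); df = n−1; exact power for the two one-sided tests.

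- Part 1: √ln(1+0.393²) = 0.379; SE = 0.379 × √(2/62) = 0.0681; power 80.2%. The smallest n reaching 80% is 62.
- Part 2: √ln(1+0.251²) = 0.247; SE = 0.247 × √(2/28) = 0.0661; power 81.4%. The smallest n is 28.

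So 62 and 28 reproduce as numbers of complete pairs, which fits the both-periods reading.

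**Worst dropout case.** Enrolment allows m = 72 − 62 = 10 and 32 − 28 = 4 non-completers. Suppose all have Period 1 data only. The documents give no within-participant correlation ρ; 0.3 to 0.7 is assumed. With n pairs and m extra Period 1 records,

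Var(all) / Var(pairs) = [(1+ρ) + (1−ρ) × n/(n+m)] / 2.

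- Part 1: n/(n+m) = 62/72 = 0.861. Ratio 0.951 (ρ = 0.3) to 0.979 (ρ = 0.7); SE 0.0664 to 0.0674 against 0.0681.
- Part 2: n/(n+m) = 28/32 = 0.875. Ratio 0.956 to 0.981; SE 0.0646 to 0.0654 against 0.0661.

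The chance movement of the primary log ratio between the two sets (one SE) is √(Var(pairs) − Var(all)): 0.98% to 1.50% in Part 1 and 0.90% to 1.38% in Part 2.

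For the probe-alone geometric mean, total log SD = within SD/√(1−ρ), which is 0.453 to 0.692 (Part 1) and 0.295 to 0.451 (Part 2). The shift is m/(n+m) × total SD × √(1/m + 1/n): 2.1% to 3.3% in Part 1 and 2.0% to 3.0% in Part 2. With 2 leavers in Part 1 or 1 in Part 2 it is 1.0% to 1.6%.

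**No dropout, outlier rule applied to every primary parameter.** Simulation: 10,000 log-normal trials per cell, 62 or 28 complete pairs, the 3-SD rule iterated within each treatment; a paired analysis compared with a random-intercept model on all remaining values.

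| | Part 1 | Part 2 |
|---|---|---|
| Trials with a one-period value for a given endpoint | 38–43% | 29–33% |
| Mean absolute shift in the ratio when that happens | 0.6–0.8% | 0.9–1.1% |
| Verdict differs, all trials, ratio 1.05, planning CV | 1.1–1.4% | 1.2–1.5% |

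Disagreement is 0.8% to 1.2% at ratio 1.00, and 0.4% to 0.8% at assumed CVs of 30% and 20% with ratio 1.05.

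Disagreement does not show that either set is wrong, so a second simulation (4,000 trials per cell) looked at operating characteristics. It gave disagreement of 1.2% to 1.7%. Mean error on the log scale agreed between the sets to within 0.0007, and power differed by 0.0 to 0.9 percentage points. At a true ratio of 1.25 and ρ = 0.5, equivalence was concluded in 5.8% (pairs) against 5.9% (all available) in Part 1, and 6.0% against 6.3% in Part 2. The excess over 5% appears under both sets, so the choice of set does not cause it.

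**The case for a change.** The strongest argument for acting is that this is the analysis set behind the primary conclusion of an open-label study, and a couple of sentences written before data are seen would remove an analyst's choice. The supersession clause in SAP section 3 could also be turned round: if the SAP overrides the protocol and names only the wider population, the both-periods rule might be taken as dropped. And dropout related to exposure could move the estimate by more than chance. In one constructed data set (62 pairs plus 10 leavers with lower Period 1 exposure, assumed between-participant CV 50%), the ratio was 1.11 (90% interval 1.00 to 1.24) with all records and 1.07 (0.96 to 1.19) with pairs only.

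Some of this stands. The SAP does not restate the rule, and the code does not enforce it. But supersession applies where the SAP says something different, and differences are to be identified. On a further restriction within the same population the SAP is silent, so the protocol stands. SAP section 9.1 applies populations only as a general rule, which leaves room for a subset. The signed-rank test for tmax and the individual rosuvastatin ratios already need pairs. In the constructed data set, both intervals lie inside 0.80 to 1.25, and Protocol section 7.2 anticipates few discontinuations.

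The no-dropout case is weaker than its frequencies suggest. SAP section 9.3.1 states that the outlier procedure is not mandatory and that a flagged value need not be removed, so 29% to 43% is an upper scenario. Protocol section 9.4.2.2 evaluates Cmax and AUC(0-∞) separately, so evaluability is naturally judged parameter by parameter. On that reading, a lone AUC(0-∞) value drops out of the AUC model.

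**Conclusion.** No change follows. This is a gap that analysts will fill sensibly, and closing it on paper would gain next to nothing. SAP section 8 settles the descriptive set by adopting the protocol's own named population. For inference, carrying over the both-periods rule is the natural reading, and it matches the pairs on which power was computed (80.2% and 81.4%).

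If an analyst used all available records instead, the result would still be usable: the standard error would be about 1% to 2.5% smaller in the worst dropout case, and the primary ratio would move by 0.9% to 1.5% (one standard error). With the optional outlier rule applied throughout, the verdict for an endpoint differs in about 0.4% to 1.7% of trials, with no material difference in bias or in false equivalence.

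These sizes rest on an assumed within-participant correlation of 0.3 to 0.7, log-normal data and, for the dropout figures, leavers who do not differ systematically from completers. The false-equivalence comparison was made at a correlation of 0.5 only. The table and figure shells, which may state the sets, were not available. The incomplete statement in SAP section 11 about ECG and C-SSRS reporting is a separate documentation matter and does not affect the PK comparisons.
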